7.3 Specifications for using the device

Refer to the Product Instruction Manual.

7.4 Monitoring plan

The following activities should take place:

- The CRF shall be checked based on the subject's original medical history and original records to ensure that the records are accurate, timely recorded and complete.
- Ensure that the study operation meets the requirements of the protocol and medical device regulations.
- Ensure that the study is conducted in accordance with the requirements of the Ethics Committee
- Ensure that the procedures for acquisition of Informed Consent Form meet the specifications.

- Conduct data monitoring for the selected subjects in each centre to ensure the authenticity and accuracy of the data.
- Complete the visit records of the centre and reasonably schedule the next visit, where necessary.

8. Statistical Considerations

8.1 Population

Full Analysis Set (FAS): set of subjects that are determined according to the "Intention To Treat" principle. Refers to all subjects who signed the Informed Consent Form, met all inclusion and exclusion criteria and were treated with Minos™ system.

Per protocol set (PPS): subset of the full analysis set. Refers to all subjects in whom Minos™ system has been successfully implanted, in whom the main evaluation indicators can be observed, and in whom no significant deviations from the study protocol have been observed.

Safety set (SS): refers to all subjects who have been enrolled and evaluated for safety.

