3.2 Project contents

The study is designed as a prospective, multi-centre, post-market, real-world observational registry study. Continuous enrollment is to be conducted for all subjects treated with Minos™ Abdominal Aortic Stent-Graft and Delivery System who meet the inclusion criteria and who voluntarily consent to participate in the study. An enrollment duration period of 24 months is expected for this project and initially, 200 subjects (170 in China and at least 30 in Europe) are to be enrolled. Patient follow up – including CT imaging - will be undertaken in accordance with the usual standard of care at participating sites, and is expected to occur at 30 days, 6 months, 12 months and 2-5 years post-procedure.

1. Primary endpoint

- Technical success rate at 12 months

2. Secondary endpoints

- Incidence of major adverse events at 30 days
- Immediate technical success rate
- Incidence of successful aneurysm treatment at 2-5 years
- All-cause mortality up to 5 years post-procedure
- Aortic aneurysm related mortality up to 5 years post-procedure
- Secondary intervention rates up to 5 years post-procedure
- Aneurysm diameter and variation in aneurysm diameter from 30 days to 5 years post-procedure
- Incidence of type I, III endoleaks from 30 days to 5 years post-procedure
- The incidence rate of stent migration, fracture, stenosis, occlusion and distortion from 30 days to 5 years post-procedure

3. Other endpoints: technical success rate of Hercules balloon and incidence of balloon rupture, where applicable.

In this study, immediate technical success rate, technical success rate at 12 months, secondary intervention rate, aneurysm diameter and variation in aneurysm diameter, and the incidence of type I and III endoleaks are used as efficacy indicators of the Minos™ Abdominal Aortic Stent-Graft and Delivery System. The incidence of 30-day major adverse events, all-cause mortality, aneurysm related mortality, stent migration, stent fracture, stenosis, occlusion and distortion are used as safety indicators of the Minos™ Abdominal Aortic Stent-Graft and Delivery System.

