7.1.5 Primary endpoint

Successful aneurysm treatment: on the basis of technical success and during the follow-up period, the absence of aneurysm rupture, continuous type I and III endoleaks after operation, aneurysm enlargement (aneurysm diameter increased by more than 5mm), secondary intervention due to endoleak, stent occlusion or migration, including open surgery and endovascular surgery. Expected secondary interventions will not be included in the analysis.

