7.1.6 Secondary endpoints

30-day major adverse events: events that meet one of the following criteria during the study:

- All-cause mortality: death of any cause occurring within 30 days of procedure.
- Intestinal ischemia: lack of sufficient blood flow in the intestine, requiring intensive drug treatment or surgical/intravascular intervention treatment.
- Myocardial infarction: the increase of one or more cardiac biomarkers (especially troponin) with evidence of myocardial ischemia: ECG changes suggesting new ischemia, or imaging evidence.
- Paraplegia: severe paralysis of lower limbs.
- Kidney failure: GFR < 15ml/min, requiring permanent dialysis, renal transplantation, or death due to renal insufficiency.
- Respiratory failure: pneumonia or respiratory failure requiring ventilator support for more than 24 hours after surgery.
- Stroke: symptoms lasting 24 hours due to cerebrovascular diseases such as hemorrhage, embolism or thrombosis.
- Blood loss > 1000 ml: estimated intra-procedural blood loss > 1000 ml.

Immediate technical success: successful introduction and withdrawal of stent graft and delivery system, with accurate positioning of stent graft, normal stent shape, no distortion, bending, stenosis and occlusion, and no accidental coverage of internal iliac artery or visceral artery.

All-cause mortality: death from any cause.

Aneurysm related death: death caused by rupture of abdominal aortic aneurysm or any operation to treat abdominal aortic aneurysm. All deaths shall be judged by the Clinical Events Committee (CEC) to determine the relevance of aneurysm, instruments or surgery.

Secondary intervention: including open and intracavitary intervention. Open surgery: Open surgery performed at any time to address a failure of endovascular treatment due to failure of stent implantation or placement, complications or other clinical conditions, or after the initial success of endovascular treatment. Secondary endovascular intervention: any intravascular surgical intervention performed to resolve complications such as endoleak, aneurysm expansion, stent occlusion, stent migration and stent defect after the implantation of Minos™ system.

Change in aneurysm diameter: including “enlargement”, which refers to an increase of aneurysm diameter greater than 5mm; “reduction”, which refers to a reduction of aneurysm diameter greater than 5mm; and “stable”, which refers to a change in aneurysm diameter less than or equal to 5mm.

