8.2 Method of statistical analysis

The SAS9.13 statistical software will be used for statistical analysis. The effectiveness analysis will be performed in Full Analysis Set and Per-Protocol Set; the demographic analysis at baseline will be performed based on the Full Analysis Set; the safety evaluation will be performed in Safety Set. Descriptive summary statistics will be provided for all data. For classified variables, the frequency, percentage and 95% accurate binomial confidence interval of for point estimation shall be calculated; for continuous variables, the mean, median, interquartile range and 95% confidence interval for point estimation will be calculated. All statistical analyses are performed at the bilateral 0.05 significance level.

Kaplan Meier survival analysis shall be performed for all-cause mortality, aneurysm-related mortality, incidence of secondary intervention and other safety indicators during follow-up period.

A complete analysis of all safety evaluations will be provided, including the following analysis:

- Total number of serious adverse events (SAE)
- Total number of device-related adverse events
- Total number of device-related serious adverse events
- Total number of adverse events (AE)
- Number and percentage of subjects with serious adverse events
- Number and percentage of subjects with device related adverse events
- Number and percentage of subjects with device related serious adverse events
- Number and percentage of subjects with adverse events

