9.3 Database locking

After completing the data review and confirming the correctness of the established database, the data administrators, principal investigators, sponsor, and monitors shall jointly review the data and complete the final definition and determination of the analysis population. The database will then be locked by the data administrator. The locked database or file may not be modified thereafter.

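### The per-protocol set excludes implantation failures, and this condition can only raise the success rates estimated in it

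*Protocol*

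**What the plan says.** Section 8.1 builds the FAS on the intention-to-treat principle. Besides consent, it asks only that subjects "met all inclusion and exclusion criteria and were treated with Minos™ system". The PPS is a subset of the FAS: "Refers to all subjects in whom Minos™ system has been successfully implanted, in whom the main evaluation indicators can be observed", and with no significant protocol deviation. Successful implantation is not defined further.

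Section 8.2 states: "The effectiveness analysis will be performed in Full Analysis Set and Per-Protocol Set". The efficacy indicators in section 3.2 include "immediate technical success rate, technical success rate at 12 months, secondary intervention rate, aneurysm diameter and variation in aneurysm diameter".

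Section 7.1.6 defines immediate technical success in two parts. The first concerns delivery and placement: "successful introduction and withdrawal of stent graft and delivery system, with accurate positioning of stent graft, normal stent shape". The second concerns the result: "no distortion, bending, stenosis and occlusion, and no accidental coverage of internal iliac artery or visceral artery". Section 7.1.5 sets the primary endpoint "on the basis of technical success" and adds freedom from rupture, persistent type I or III endoleak, enlargement and certain reinterventions.

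Section 8.5 imputes the primary endpoint when it is missing because of premature withdrawal. Section 9.3 has data administrators, principal investigators, sponsor and monitors "jointly review the data and complete the final definition and determination of the analysis population" before the database is locked.

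**The concern.** A per-protocol set normally removes subjects who departed from the protocol. This one also removes subjects in whom the device could not be successfully implanted, which is a result of the treatment under study. That result is part of immediate technical success and, through the technical-success requirement, part of the primary endpoint. A subject excluded on this ground is a failure on both. The numerator stays the same and the denominator shrinks.

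At stake is what the PPS figure means. Placed beside the FAS figure, it would normally be read as a check on robustness. Here part of any difference comes from the definition of the set, and that part always favours the device.

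**Working it through.** **Inputs from the protocol.** Planned N = 200 (section 8.3, stated not to rest on statistical considerations, so there is no derivation to reproduce). The earlier investigation of the device (section 4) reports 12-month clinical success of 121/136 and all-cause mortality of 10/136. Check: 121/136 = 88.97% and 10/136 = 7.35%, matching the printed 89% and 7.4%.

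**Assumptions, not in the protocol.** The success rate in this registry equals the earlier 89%, so S = 0.89 × 200 = 178. Implantation failures number f = 2, 4 or 10 (1%, 2%, 5%). Other rates are varied below.

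**Step 1: the implantation condition and the primary endpoint.** Each implantation failure is an endpoint failure, so excluding f of them leaves S unchanged:

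PPS rate = S / (N − f), which exceeds S / N whenever f > 0.

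| f | Rate | Exact 95% CI | Gain (points) |
|---|---|---|---|
| 0 (FAS) | 178/200 = 89.0% | 83.8 to 93.0 | – |
| 2 | 178/198 = 89.9% | 84.8 to 93.7 | 0.9 |
| 4 | 178/196 = 90.8% | 85.9 to 94.5 | 1.8 |
| 10 | 178/190 = 93.7% | 89.2 to 96.7 | 4.7 |

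**Step 2: the implantation condition and immediate technical success.** Let t be the number of immediate technical failures and c the number of these that the condition excludes. Then PPS rate = (N − t) / (N − c).

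| t | c = 0 | c = half | c = about three quarters | c = all |
|---|---|---|---|---|
| 10 | 190/200 = 95.0% | 190/195 = 97.4% | 190/192 = 99.0% | 190/190 = 100% |
| 20 | 180/200 = 90.0% | 180/190 = 94.7% | 180/185 = 97.3% | 180/180 = 100% |

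The result depends on c, which the protocol does not fix because successful implantation is undefined.

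**Step 3: the observability condition.** This selects on missing data and not on the outcome. With m unobserved subjects, of whom s would have been successes, PPS rate = (S − s) / (N − f − m).

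- f = 4, m = 20, all unobserved would have succeeded: 158/176 = 89.8%.
- f = 4, m = 20, unobserved resemble the rest: 90.8%, as in step 1.
- f = 4, m = 20, all 18 remaining failures are unobserved: 176/176 = 100%.
- f = 2, m = 40, all unobserved would have succeeded: 138/158 = 87.3%, below the 89.0% of the FAS.

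The direction is not fixed. If the main evaluation indicators include the primary endpoint, as one would read them, a subject without it is outside the PPS. The imputation in section 8.5 then has nobody to act on in that set.

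**The case against.** The strongest reply is that the unselected estimate is already planned. The FAS has no success condition, and section 8.2 reports effectiveness in it alongside the PPS. Section 8.3 describes a descriptive study with no hypothesis test, so no pass or fail decision turns on the PPS. This stands, and it limits the severity. It does not repair the PPS rates, which the protocol itself calls for.

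Several stronger readings are tempting, and the documents do not support them:

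- **PPS immediate technical success is 100% by construction.** A graft that was implanted can still fail on distortion, bending, stenosis, occlusion or accidental branch coverage. Exactly 100% follows only if the two definitions coincide.
- **The PPS rate as a whole can only move upward.** That is true of the implantation condition alone. The observability condition is a common per-protocol criterion and can act either way (step 3).
- **The set definition alone adds about 7 points.** This comes from removing the 10 deaths of the earlier study from its 15 non-successes: 121/126 = 96.0%. The protocol does not say that the deaths were non-successes, and section 7.1.5 does not list all-cause death as a failure. If 5 of the 10 had counted as successes, the figure is 116/126 = 92.1%. If all 10 had, it is 111/126 = 88.1%, below the 89.0% overall.
- **The more favourable set will be headlined, because neither is named as primary.** Which set leads may be left to the SAP, which is not at hand, so this is no defect of the protocol.
- **The sets will be tailored to the results under section 9.3.** Nothing shows this. Data administrators and monitors share that review, and section 7.1.3 provides independent data management and analysis, an independent event committee and blinded image reading. The narrower point stands: section 9.3 leaves the definition, and not only its application, to be completed after the data have been reviewed.

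**Conclusion.** The concern holds for the implantation condition, and its severity is moderate. The direction is certain: the condition cannot lower the PPS rates for the primary endpoint or for immediate technical success, and it raises them as soon as one implantation failure occurs. The size is not known from the documents. Under the assumed 89% success and 1% to 5% implantation failures in 200 subjects, the primary-endpoint rate rises by 0.9 to 4.7 points. For immediate technical success the inflation runs from nothing to the full failure rate, according to the overlap of the two definitions. The observability condition is a separate selection of unknown direction that also makes the planned imputation idle in the PPS. The FAS estimates are unaffected by the implantation condition.

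**What to change.** - **Section 8.1:** delete the implantation-success condition. Define the PPS as FAS subjects without a major protocol deviation from a prespecified list. Section 14 counts some failures to assess the primary endpoint as major deviations, so the list should say whether a missing endpoint excludes a subject. If it does, section 8.5 should say that the imputation applies to the FAS only.
- **Section 8.2:** treat the FAS as the primary effectiveness set. Report immediate technical success in all subjects in whom implantation was attempted, that is, in the FAS and not in the PPS. A short statement that treated includes attempted would make this explicit.
- **Section 9.3:** have the review before lock apply the written set rules, in place of completing their definition after the data have been seen.

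The cost is a wording change, with no added data collection or subjects. The PPS success rate will be slightly less favourable than under the present definition.

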7.1.4 Selection of subjects

Inclusion criteria

To be enrolled, patients must meet all the following criteria:

- Diagnosis of infrarenal abdominal aortic aneurysm
- Plan to treat with Minos™ Abdominal Aortic Stent-Graft and Delivery System
- Voluntary participation and completion of Informed Consent Form, with willingness to participate in follow-up to 5 years post-procedure.

Exclusion criteria

- Subjects in whom use of the Minos™ Abdominal Aortic Stent-Graft and Delivery System is contraindicated.

Indications:

- Abdominal Aortic Stent-Graft and Delivery System is indicated for the treatment of abdominal aortic aneurysms with a proximal neck length ≥ 15 mm.
- **Contraindications:**
 - Severe stenosis or calcification near the aneurysm, leading to difficulty in achieving apposition of vessel wall and stent graft.
 - Difficult access due to severe stenosis or tortuosity in the iliac artery or femoral artery
 - Subjects with ruptured aneurysm or acute aneurysm
 - Subjects with an infectious aneurysm.
 - Those who are allergic to contrast agents or unable to tolerate contrast agents due to renal insufficiency.
 - Patients with severe coagulation disorder and/or high risk of postoperative hemorrhage.
 - Aneurysmal neck angulation greater than 60°
 - Patients with blood supply to vital organs originating from the aneurysmal sac.
 - Patients with other comorbidities and whose life expectancy does not exceed one year
 - Subjects with connective tissue diseases, such as Marfan syndrome
 - Minors and pregnant women
 - Subjects who are allergic to nitinol
 - Subjects who are considered not suitable for treatment with stent graft.

Criteria and procedures for termination of the study/treatment

- Should severe safety concerns arise, the study shall be suspended in time.
- If the therapeutic efficacy of the investigational device is found to be poor or ineffective such that it is of no clinical value, the study shall be suspended.
- The discovery of major errors in the clinical trial protocol or significant deviation from it, making it difficult to evaluate the safety and efficacy of the investigational product.
- The sponsor requests suspension (for the reason of funds, management, etc.)
- Revocation is issued by the approving authorities.

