7.2 Study Process

1. Case registration: The Internet registration system will be utilized to register all eligible patients who have been treated with Minos Abdominal Aortic Stent-Graft and Delivery System and who have voluntarily consent to participate in the study.
2. Signing the Informed Consent Form
3. Case screening: Cases are selected according to inclusion and exclusion criteria;
4. Case enrollment
5. Collecting the preoperative and intraoperative data
6. Postoperative follow-up: Imaging follow-up to be conducted in accordance with standard of care at participating sites, to include at 30 days, 6 months, 12 months and annually to 5 years after post-procedure. It is expected that all patients will complete this follow up schedule, but participants will not be excluded in the event that follow up is not completed.
7. Data analysis and summary: All relevant data will be collected and analysed from time to time as the study progress.

Flow chart of study:

Project	Visit1	Visit2	Visit3	Visit4	Visit5	Visit6	Visit (7-10)
Time points	Preoperative	Intraoperative	Discharge	30 days after surgery	6 months after surgery	12 months after surgery	2/3/4/5 years after surgery
Window period ³				±7d	±30d	±60d	±90d
Informed consent ¹	X						
Demographics	X						
Inclusion criteria	X						
Baseline / Disease history	X						
Physical examination	X						
Blood test ²	X		X				
CT	X			X ^{4, 5}	X ⁴	X ⁴	X ⁴
Record of operation process		X					
Evaluation of adverse event		X	X	X	X	X	X

Note:

1. The subjects shall complete the signing of the Informed Consent Form before enrollment into the study. This will ideally be prior to the treatment procedure. The absence of laboratory test and imaging examination shall not be considered as a protocol deviation.
2. Blood examination includes standard of care tests in the study site, likely full blood count and standard liver and kidney function tests.
3. CT images collected outside of the follow-up window after surgery will not be considered as a protocol deviation.
4. CT imaging may not be undertaken at all follow up points if it is not the treating institution's standard of care to do so. In such cases, alternative imaging can be recorded i.e. USS.

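### The Safety Set carries no device-exposure condition, so enrolled patients who never receive Minos can enter the safety denominators

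*Protocol*

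**What the plan says.** Protocol section 8.1 defines three analysis sets. The Safety Set is defined by enrolment plus a safety evaluation: "Safety set (SS): refers to all subjects who have been enrolled and evaluated for safety". The Full Analysis Set is limited to consented subjects who "met all inclusion and exclusion criteria and were treated with Minos™ system". Section 8.2 then directs that "the safety evaluation will be performed in Safety Set".

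Section 3.2 names the outcomes that count as safety: "The incidence of 30-day major adverse events, all-cause mortality, aneurysm related mortality, stent migration, stent fracture, stenosis, occlusion and distortion are used as safety indicators". Section 8.2 adds the counts and percentages of subjects with adverse events, serious adverse events and their device-related subsets.

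On who is enrolled, and when, the protocol says two things:

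- **Before treatment.** The device criterion in section 7.1.4 is "Plan to treat with Minos™ Abdominal Aortic Stent-Graft and Delivery System". Section 7.2, note 1, puts consent before enrolment and adds: "This will ideally be prior to the treatment procedure". The flow chart places consent and the inclusion check at the preoperative visit, and the process list puts enrolment ahead of collecting intraoperative data.
- **After treatment.** Section 3.2 states: "Continuous enrollment is to be conducted for all subjects treated with Minos™ Abdominal Aortic Stent-Graft and Delivery System". Step 1 of section 7.2 is to "register all eligible patients who have been treated with Minos Abdominal Aortic Stent-Graft and Delivery System". Section 7.1.2 describes registration in similar terms.

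**The concern.** The safety rates of this registry are meant to describe the Minos device. A population for that purpose should be defined by exposure. As written, a patient who is enrolled on the intention to use Minos, and who then receives another graft, has open repair with no Minos attempt, or has no operation, qualifies once any safety check is recorded.

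Such a patient distorts the rates in one of two ways. For outcomes that need an implanted stent (migration, fracture, stenosis, occlusion, distortion), the patient cannot have the event and only enlarges the denominator. For outcomes that can follow any treatment (death, serious adverse events, most 30-day major adverse events), the patient can also contribute an event that Minos did not cause. The registry has no control arm and few expected early events, so even one such event is visible in the reported percentage.

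**Working it through.** **Step 1. Compare the definitions.** No sample size, power or alpha figure is involved: section 8.3 says the 200 does not rest on statistical considerations. The question is whether a subject can be enrolled and yet unexposed.

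| Element | Exposure to Minos required? |
|---|---|
| Device inclusion criterion (7.1.4) | No, an intention suffices |
| Consent and enrolment (7.2, note 1 and process list) | No, ideally before the procedure |
| Description of enrolment and registration (3.2, 7.1.2, 7.2 step 1) | Yes |
| Full Analysis Set (8.1) | Yes |
| Safety Set (8.1) | Not stated |

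The first two rows allow an enrolled, unexposed subject. The third excludes one. The Safety Set sentence does not say which reading applies.

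**Step 2. Identify the outcomes reached.** Section 13.1 ties an adverse event to treatment with the investigational device, so a complication of another treatment should not be counted as an adverse event or as device-related. Section 13.2 (serious adverse events, reportable whether or not related to the product) and section 7.1.6 (30-day major adverse events, death from any cause) contain no such tie. Misattributed events therefore reach mainly those outcomes; for the stent-specific outcomes the effect is dilution only.

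**Step 3. Size of dilution.** Inputs: N = 200 (section 7.1.4) and the pre-market 30-day major adverse event rate of 2/136 = 1.47% (section 4, given as 1.5%). Expected events: 200 × 2/136 = 2.9, taken as 3. The number unexposed, u, is an assumption. With all 3 events among the exposed, the exposed-only rate is 3/(200 − u), the Safety Set rate is 3/200, and the relative dilution is u/200.

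| u (assumed) | Exposed only | Safety Set as written | Relative dilution |
|---|---|---|---|
| 0 | 3/200 = 1.50% | 1.50% | 0% |
| 5 | 3/195 = 1.54% | 1.50% | 2.5% |
| 10 | 3/190 = 1.58% | 1.50% | 5% |
| 20 | 3/180 = 1.67% | 1.50% | 10% |

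The largest shift is 1.67 − 1.50 = 0.17 percentage points. The exact 95% interval for 3/200 is 0.31% to 4.32%, far wider than the shift.

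The same formula at the pre-market 12-month mortality of 10/136 = 7.35%, with 10 unexposed and 14 deaths among the 190 exposed, gives 14/190 = 7.37% against 14/200 = 7.00%.

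**Step 4. Size of one misattributed event.** One major adverse event in an unexposed patient turns 3/200 = 1.5% into 4/200 = 2.0%, a relative increase of (4 − 3)/3 = one third. Taking that patient out of the denominator as well gives 3/199 = 1.51% as the comparison, which changes nothing of substance.

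**The case against.** The strongest reply is that enrolment already implies exposure, because sections 3.2, 7.1.2 and 7.2 speak of treated patients. In practice this may keep unexposed subjects few or absent, and a patient who consents after the procedure is exposed by construction. But that wording conflicts with the inclusion criterion and with preoperative enrolment, and it is not carried into the Safety Set. The neighbouring Full Analysis Set states exposure expressly.

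A second reply is that section 9.3 leaves final determination of the analysis populations to data review before lock, and that a statistical analysis plan may add detail. Detail may indeed be left there. Here, however, the protocol states a rule, and the rule omits the condition that matters. Nor can the Full Analysis Set stand in for safety: it also requires that all eligibility criteria were met, so it can drop treated patients.

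A third reply is that the effect is negligible in a descriptive study with no hypothesis test. On dilution this is largely right.

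Two stronger readings are tempting, and the documents do not support them:

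- A reader might infer that exposed patients drop out for lack of a safety evaluation, lowering the rates. The flow chart schedules adverse event evaluation during the operation and at discharge, so almost no exposed, enrolled patient would lack one. A recorded event is itself a safety evaluation. An event nobody observed would not be recovered by redefining the set, since only the denominator would grow.
- A reader might infer that every device outcome is affected. Section 3.2 classes secondary intervention and type I and III endoleak as efficacy indicators, which section 8.2 assigns to the Full Analysis and Per Protocol Sets, although section 8.2 also groups secondary intervention with safety indicators for the Kaplan–Meier analysis. The point is limited to indicators analysed in the Safety Set.

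**Conclusion.** The point holds in limited form and is minor. The Safety Set lacks an exposure condition, the protocol's statements about enrolment disagree, and an enrolled patient who never receives Minos can be counted in device safety rates. Dilution equals the unexposed share: at most 0.17 percentage points on a 1.5% rate with up to 20 of 200 unexposed. A single misattributed major adverse event would matter more, moving 1.5% to 2.0%. Both figures rest on assumed counts, since the protocol does not say how many enrolled patients are expected to go untreated, and on an event rate borrowed from the pre-market study. If every enrolled patient is in fact treated with Minos, the effect is nil.

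**What to change.** Replace the Safety Set sentence in section 8.1 with a definition by exposure, for example: *Safety Set: all enrolled subjects in whom use of the Minos system was attempted, whether or not a graft was implanted, with follow-up counted to last contact.* State what counts as an attempt, such as introduction of a Minos delivery system into the vasculature. List enrolled but unexposed subjects separately, each with the reason.

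In the same edit, reconcile sections 3.2, 7.1.2, 7.1.4 and 7.2 on whether enrolment precedes or follows treatment.

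The cost is one sentence, one listing and a wording alignment. No new data are needed, because the operation record already shows whether Minos was used.
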